9.2 SAMPLE SIZE DETERMINATION

Power Analysis For Pre-Post Trial – Under the assumption of 24 clinics, at least 500 eligible MHS patients in each clinic in each six-month period, a rate of documented OUD of 1% pre-screening, a conservative estimate of 0 correlation between pre- and post-percentages, and an alpha significance level of 0.05, we will have 80% power to detect an increase from a pre-screening percentage of 1% to a post-period percentage of 1.7%.

Power Analysis For Effectiveness Trial - Assuming a coefficient of variation of 0.33 for the continuous outcome of days of illicit opioid use⁶⁷⁶ and SF12V MCS scores⁶⁶⁸⁷, a highly conservative intraclass correlation within clinics of 0.03, 12 clinics per group and 40 patients per clinic (n=960, accounting for NIH Behavioral and Social Intervention Clinical Trial Protocol Template v3.0 - 20180827

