20% attrition), we will have 80% power to detect an effect size of 0.31. We chose to use a highly conservative intraclass correlation to ensure sufficient power for secondary outcomes and mediation analyses (Hypothesis 2b). Thus, conservatively we will have 80% power to detect a 10 % difference in number of days using illegal opioids in the past month (e.g., 15.00 days compared to 13.5 days) and 10% difference in MCS scores (e.g., 40 compared to 36) between CHAMP and CoCM for MHS only clinics. Because these are multiple primary outcomes (and not co-primary outcomes), this power analysis assumes a Bonferroni correction for the two multiple primary outcomes. Specifically, the intervention will be interpreted to have been successful if there is a significance group different between either primary outcome, not both primary outcomes. Because of recruitment challenges, power analyses are also now provided for the lower bounds of expected enrollment. The lower-bounds power analysis assumes that we will recruit 360 study participants instead of 1200. For this lower-bounds power analysis, we assume a more realistic intraclass correlation of 0.01 instead of 0.03. Collaborative care trials conducted by [name] (MPI) and [name] (NIMH collaborator) found intraclass correlation coefficients in the range of 0.008-0.001).^{30,66} Assuming a coefficient of variation of 0.33 for the continuous outcome of days of illicit opioid use⁶⁷ and SF12V MCS scores⁶⁸, an intraclass correlation within clinics of 0.01, 12 clinics per group, 15 patients enrolled per clinic (n=288 accounting for 20% attrition), we will have 80% power to detect an effect size of 0.41. The sample size of 360 does not represent a revised enrollment target, and we will continue to enroll as many study participants as possible (up to 1,200) using enhanced recruitment methods and by extending the recruitment period if possible.

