variable of interest will be group randomization status (e.g., intervention versus control). Main effects and interaction terms with time-indicator variables capture the difference between intervention and control group at each wave. Covariates will be included if they are theoretically related to both the dependent variable and the probability of having missing data. An alpha level of 0.05 and two-tailed tests will be used to determine statistical significance. Results will be presented as adjusted differences between groups with confidence intervals. **Missing Data** - We will examine patterns of missing data to determine the degree to which the missing at random assumption (the degree to which missingness is related to variables included in the model) is plausible. With high missing rates, we may use missing data methods to account for missing not at random mechanisms. If warranted, multiple imputation or similar methods will be used to account for missing data on completed or partially completed baseline and follow-up surveys (e.g., skipped items).

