Primary outcome. There are two primary outcomes (see Table 1). Opioid use is one of our primary outcomes and is measured using item 7E from the Brief Addiction Monitor-Revised (BAM-R) which was derived from the Addiction Severity Index35 by CESATE: “7. In the past 30 days, how many days did you use any of the following drugs: E. Opiates (e.g., Heroin, Morphine, Dilaudid, Demerol, Oxycontin, oxy, codeine (Tylenol 2,3,4), Percocet, Vicodin, fentanyl, etc.)?” Our other primary outcome is mental health related quality of life and is being measured using

the Veterans Short Form Health Survey 12 Mental Health Component Summary score (MCS). Both primary outcomes are assessed at the 6-month follow-up survey.

Secondary outcomes. This study includes 24 secondary outcomes, assessed at both the 3-month follow-up and the 6-month follow-up (Table 1). Secondary outcomes include the use of other drugs, depression, anxiety, PTSD, pain, physical health-related quality of life and perceived access to OUD care (see Table 1). Secondary outcomes also include opioid use and mental health related quality of life assessed at the 3-month follow-up survey. Exploratory outcomes are risk factors for premature mortality, including suicidal ideation, discontinuing MOUD, overdose, suicide attempts, emergency department admission, and hospitalization. Risk factors are collected via survey and adverse event reporting.

Construct/Instrument	Instrument(s)	Baseline	3-Month Follow-Up	6-Month Follow-Up
Multiple Primary Outcomes				
Opioid Use	BAM-R ^{1,2}	X	X	X
Mental health related quality of life (MCS)	Veterans Short Form-12 ³	X	X	X
Secondary Outcomes				
Pain	PEG ⁴	X	X	X
Alcohol Use	AUDIT-C ⁵	X	X	X
Cannabis Use	BAM-R ^{1,2}	X	X	X
Other Drug Use	BAM-R ^{1,2}	X	X	X
Depression	SCL-20 ⁶	X	X	X
Anxiety	PROMIS Measure - Anxiety, Short Form ^{7,8}	X	X	X
PTSD	PCL-5 ^{9,10}	X	X	X
Physical health related quality of life (PCS)	Veterans Short Form-12 ³	X	X	X
Access to Care	APAC ¹¹	X	X	X
Exploratory Outcomes				
Risk factors for mortality	WFS ¹ and Adverse Events	X	X	X
Mediator Variable				
MOUD Consistency	WFS ¹	X	X	X

APAC - Assessment of Perceived Access to Care

BAM-R - Brief Addiction Monitor-Revised

ICR - Individual Change Readiness

MOUD – Medications for Opioid Use Disorder

PCL-5 - PTSD Check List

PC-PTSD-5 – Primary Care PTSD Screen for DSM-5

PCS - Physical health related quality of life

PEG - Pain, Enjoyment of Life and General Activity

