
For the primary outcome (mental health related quality of life [0-100]) we will use a linear mixed model with a normal distribution with a linear link function and model structure given above in Equation 1. For the primary outcome days-using-opioids [0-30] we will modify the above linear mixed model and adopt a similar regression structure using a generalized linear mixed model with binomial distribution logit link function. We will retain the random effect structure to include a random effect for clinic and include the time-specific subject-level error terms to both allow for binomial overdispersion and a general longitudinal covariance over time. For the secondary and exploratory outcomes, appropriate link functions will be used for linear, binary (logit), ordinal (logit), and count (Poisson/negative binomial depending on dispersion) data. For any binary longitudinal outcomes, we will simplify the subject-level random effects to be a simple random intercept due to identifiability (no overdispersion and only correlation).

Effect sizes. Cohen's d effect sizes will be calculated and presented with 95% confidence intervals. Between group effect sizes will be calculated as the model-estimated treatment effect at each time point divided by the pooled, raw baseline standard deviation.

Testing of Multiple Primary Outcomes. The intervention will be interpreted to have been successful if there is a significance group difference between either primary outcome, not necessarily both primary outcomes. Corrections for multiple testing will be computed using a Bonferroni correction for the two multiple primary outcomes and therefore we will use an $\alpha=0.05/2 = 0.025$ to test each primary outcome. All secondary outcomes are exploratory and no multiple testing adjustment will be used. We will present secondary and exploratory outcomes descriptively using a forest plot to illustrate the collection of associations with intervention.

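### The SAP's Bonferroni rule for the two primary outcomes is valid but less efficient than Holm, and protocol 9.4.1 and 9.4.2 give 0.05 without the correction

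*SAP*

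**What the plan says.** The two primary outcomes are days of opioid use and the mental component score (MCS). On timing, SAP section 3 says: "Both primary outcomes are assessed at the 6-month follow-up survey". The success rule in SAP 4.1 is disjunctive: "The intervention will be interpreted to have been successful if there is a significance group difference between either primary outcome, not necessarily both primary outcomes". For multiplicity the same section says "Corrections for multiple testing will be computed using a Bonferroni correction for the two multiple primary outcomes", and it sets 0.05/2 = 0.025 for each outcome. It gives no step-down rule.

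Protocol 9.2 agrees with the SAP: "this power analysis assumes a Bonferroni correction for the two multiple primary outcomes". Protocol 9.4.2, which describes the primary analysis, says only: "An alpha level of 0.05 and two-tailed tests will be used to determine statistical significance". Protocol 9.4.1 says the same for statistical tests in general, and 9.4.3 repeats it for the secondary outcomes. None of these three sections mentions the correction.

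SAP Table S2 has columns for 95% intervals and none for p-values.

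**The concern.** There are two separate issues.

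**Efficiency.** The trial asks about opioid use and about mental health functioning, and Table S2 reports each. Bonferroni holds both tests at 0.025 whatever the other shows. Holm tests the smaller p-value at 0.025 and, if that is significant, the other at 0.05. It rejects everything Bonferroni rejects and sometimes more, at the same family-wise error under any dependence. The power given up concerns the second conclusion, in a trial that enrolled 254 patients (SAP section 6) against a target of 1,200 (protocol 1.1).

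**Consistency.** Suppose one outcome has a p-value between 0.025 and 0.05 and the other is above 0.05. On a literal reading of protocol 9.4.2 with the either-outcome rule, the trial succeeds. Under the SAP it does not. The two public documents should not allow both answers.

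**Working it through.** **Step 1. Which level do the plan's own power figures use?**

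Inputs from protocol 9.2: 12 clinics per arm, 40 patients per clinic, 960 analysed, "a highly conservative intraclass correlation within clinics of 0.03", and the result "we will have 80% power to detect an effect size of 0.31".

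- Design effect = 1 + (m − 1) × ICC = 1 + 39 × 0.03 = 2.17.
- Standard error in SD units = √(4 × 2.17 / 960) = 0.0951.
- Non-centrality = 0.31 / 0.0951 = 3.26, with t on 24 − 2 = 22 degrees of freedom.
- Power at two-sided 0.025: 79.7% (minimum detectable effect 0.311). Power at two-sided 0.05: 87.6%.

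The lower-bound scenario (288 analysed, 12 per clinic, ICC 0.01, design effect 1.11, effect 0.41) gives 80.8% at 0.025 and 88.4% at 0.05. Both scenarios reproduce the stated 80% at 0.025 and not at 0.05.

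**Step 2. Family-wise error with both nulls true and independent tests**

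- 0.025 each: 1 − 0.975² = 0.0494.
- 0.05 each: 1 − 0.95² = 0.0975.
- Holm: the same as Bonferroni, because a first rejection under Holm needs a p-value below 0.025.

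With one null true and the other effect at its planned size, simulated error on the true null under Holm is at most about 0.045.

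**Step 3. Power when both effects are real**

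Assume each outcome has 80% power at 0.025.

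- Non-centrality = 2.241 + 0.842 = 3.083.
- Power of a single test at 0.05 = Φ(3.083 − 1.960) = 86.9%.
- Holm, per outcome, independent tests: p₂₅ + (p₀₅ − p₂₅) × p₂₅ = 0.800 + 0.0693 × 0.800 = 85.5%.
- Both outcomes, Bonferroni: 0.80² = 64%.
- Both outcomes, Holm: p₀₅² − (p₀₅ − p₂₅)² = 0.7557 − 0.0048 = 75.1%.

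The documents do not give the correlation between the two test statistics, so a range is assumed. The correlated rows come from 2 million simulated pairs.

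| Correlation (assumed) | Per outcome, Bonferroni → Holm | Both, Bonferroni → Holm | At least one, either method |
|---|---|---|---|
| 0 | 80% → 85.5% | 64% → 75% | 96% |
| 0.3 | 80% → 85.0% | 67% → 77% | 93% |
| 0.5 | 80% → 84.6% | 69% → 78% | 91% |
| 0.8 | 80% → 83.8% | 73% → 80% | 87% |

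The last column is the trial's success rule. It does not change.

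**Step 4. Power in less favourable cases (independent tests)**

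- Only one effect real: the gain on it is 0.025 × (86.9% − 80.0%), or about 0.2 points.
- Both effects half the planned size: non-centrality 1.542, p₂₅ = Φ(1.542 − 2.241) = 24.2%, p₀₅ = Φ(1.542 − 1.960) = 33.8%. Holm gives 0.242 + 0.096 × 0.242 = 26.5%, a gain of about 2 points.

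**The case against.** The case for leaving the plan alone is substantial.

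- **Bonferroni is prespecified, valid and in line with protocol 9.2.** This stands. A reader might infer that the primary analysis is wrong or that the success claim loses power. The documents support neither: error is controlled, and the chance of success on at least one outcome is the same under Holm.
- **The size of the gain is a favourable case.** This stands in part. Step 3 needs both effects to be real at the planned size. The 80% premise is also less secure for MCS. With the SAP's 254 patients, 28 clinics, ICC 0.03 and cluster-size coefficient of variation 0.97 (design effect 1.50), an effect of 0.46 has 73% (t) to 77% (normal) power at 0.025.
- **Protocol 0.05 may be the overall level.** A reader might infer that the trial will test both outcomes uncorrected. The documents do not support that: protocol 9.2 applies Bonferroni, 9.4.1 defers to a formal SAP, the SAP fixes 0.025, and Step 1 confirms it. But 9.4.2 does not call 0.05 an overall level, and 9.4.3 uses the same sentence for outcomes the SAP leaves unadjusted. The wording still needs repair.
- **Timing.** Moving to a rule that never rejects less is credible only before results by arm are seen. The SAP change log entry of 6/18/24 explains a change by intervals that include zero although the effect is significant. The entry of 8/30/24 drops a covariate to help convergence. A reader might infer that results by arm were known. The entries do not establish this, and SAP section 6 places its power calculation before unmasking. They do leave the status uncertain.
- **Intervals.** Bonferroni has matching 97.5% intervals; Holm has no equally simple counterpart. This stands as a small cost. The 95% intervals in Table S2 match neither rule: with p-values of 0.03 and 0.20, one interval excludes the null although neither method rejects.

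**Conclusion.** The point holds as one of efficiency and consistent wording, not as an error in the SAP's test.

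Holm would add about 4 to 5.5 points of power per outcome and about 7 to 11 points for showing both, at the same family-wise error. This assumes that both effects are real, that each has 80% power at 0.025, and that the correlation lies between 0 and 0.8. The gain is about 2 points if both effects are half that size (independent tests) and close to nil if only one is real.

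The 0.05 sentence in protocol 9.4.1 and 9.4.2 conflicts with protocol 9.2 and the SAP. The family-wise error of about 9.75% follows only if that sentence is applied literally to each of two independent tests. It measures what the ambiguity would permit and is not a forecast of what the analysts will do.

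**What to change.** 1. **Protocol 9.4.1 and 9.4.2, whatever the masking status.** Change the 0.05 sentence so that, for the two primary outcomes, it refers to the multiplicity rule in SAP 4.1. This only tightens the protocol and cannot favour the intervention.
2. **Confirm and record whether anyone involved in the analysis has seen outcome data by arm.**
3. **If the data are still masked:** in SAP 4.1 replace Bonferroni with Holm at family-wise two-sided 0.05. Add Holm-adjusted p-values to Table S2, with a note that its 95% intervals are not adjusted for multiplicity.
4. **If results by arm have been seen:** keep 0.025 each as the confirmatory rule and show Holm-adjusted p-values only as a labelled supplement.

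The cost is a few sentences and one table column. The price of Holm is the lack of simple matching intervals, which the table note makes plain.

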4.2 Moderated Mediation Analyses (Hypothesis 2)

Hypothesis 2: MOUD consistency will fully mediate any improvements in patient-reported outcomes observed in intervention clinics compared to control clinics.

These analyses will compare the different pathways through which the intervention transmits effects. We hypothesize that the intervention should lead to greater use of MOUD (A path in Figure 2) because of the care managers' encouragement of MOUD initiation and adherence, leading to improved outcomes. We also expect the intervention will cause MOUD use to be more effective (Moderation path in Figure 3) in improving outcomes because of the use of the OTRI measurement-based care instrument and dosage recommendations by the consulting psychiatrist. Because the proposed moderation violates the assumption of mediation, we will first test the moderation (Figure 3), followed by a mediation or moderated mediation analysis (Figure 2).^{13,14} This analysis will be performed in three stages. In the first stage, we will use the same model as described in equation 1 to assess the MOUD consistency x intervention (moderator) interaction (Figure 3) (Table S4a). In the second stage, we will test the effect of the intervention on the mediator (A path in Figure 2) (Table S4b). In the third stage, the mediator will be included (B path), controlling for the direct effects of treatment (C path in Figure 2) (Table S4b). If the moderation is statistically significant, the MOUD consistency x intervention interaction will be included in this model. Models will be run separately for 3- and 6-months.

Figure 2. Path diagram for mediation model

[figure not shown]
[figure not shown]

Figure 3. Path diagram for moderation model

For the moderation analysis, we use the same model structure and design variables as the primary outcome. We will include MOUD consistency and intervention as main effects and the MOUD Consistency x intervention interaction. (Table S4a).

To calculate A path, the main effect of treatment on the mediator, we will use the same model as the primary outcome (Table S4b). Direct effects on MOUD consistency (path A) will be presented as an adjusted mean. To account for the potential imbalance of the mediator across the intervention and control groups at baseline due to the small number of clusters, the main effect for intervention at baseline is included.

To calculate the B and C paths, we will include the mediator and intervention-mediator interaction in predicting outcomes (Table S4b). To calculate the total effect of the mediator for the intervention, we will sum the main effects and interactions. To calculate indirect effects (Table S4b), we will multiply the A path by the B path for the mediator. Because the distribution of the product may be non-normal, we will calculate 95% confidence intervals using bootstrapping.

5. Missing data

Estimates from multilevel models are unbiased under conditions of *Missing at Random* (MAR), which means that the mechanism that causes missingness is included in the model. Most relevant to the current analysis, in longitudinal data, estimates will be unbiased when

missingness is caused by previously observed values of the dependent variable, but not if missingness is caused by the unobserved value at the missing wave. We will attempt to make the MAR assumption more plausible by incorporating reasons for missingness into the model. We will analyze data with maximum likelihood estimation (MAR assumption) and no auxiliary information.¹⁵

6. Power Calculation

The DSMB directed the research team to discontinue consenting new patients into the trial for reasons of futility due to the current rate of recruitment. Therefore, we present a revised power analysis calculated before the outcome data are to be unmasked. The revised power analysis is based on the observed number of patients enrolled (n=254), observed number of clinics enrolling ≥ 1 patient (n=28), the observed coefficient of variation (0.97) which represents the variation in cluster sizes, and the Intraclass Correlation Coefficients (ICCs) estimated for interim analysis requested by the DSMB. For the masked interim ICC estimation we used all patient data available on 11/7/2022, including N=191 in the baseline sample and N=155 in the 6-month follow-up sample. We adjusted for treatment group and baseline primary outcomes. We used the jackknife method to compute a standard error by computing ICCs deleting each cluster in turn and then averaging these estimates.¹⁶ For the 6-month follow-up, the opioid use ICC was estimated to be 0.00 (SE= 0.02). For the 6-month follow-up, and the MCS ICC was estimated to be 0.03 (SE=0.09). Based on these estimates, and using a Bonferroni correction to account for multiple outcomes, we will have 80% power to detect a medium effect size of 0.40 for days of opioid use and a medium effect size of 0.46 for MCS. This represents a difference of 2.65 (e.g., 15.00 days compared to 12.3 days) days using opioids and a difference of 6.22 (e.g., 40 compared to 33.8) on the MCS between the intervention and control groups.

7. References

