3 OBJECTIVES AND ENDPOINTS

OBJECTIVES	ENDPOINTS
Primary	
Objective: Compare patient-reported outcomes in the intervention and control groups.
 
Hypothesis a: Compared to patients with MHS and OUD at clinics randomized to the control, patients at clinics randomized to the intervention group will have better patient-reported outcomes.
 
Hypothesis b: Persistent use of MOUD will completely mediate any improvements in patient-reported outcomes observed in intervention clinics compared to control clinics.

Secondary	
Objective: Compare the Detection of OUD pre-versus post-OUD screening implementation.
 
Hypothesis: The proportion of patients enrolled in the clinic with a MHD diagnosis and a new OUD diagnosis documented in the electronic medical record will be higher in the post-period than the pre-period.

Tertiary/Exploratory	
Objective: To conduct a pre-post evaluation (quantitative and qualitative) of a high-intensity sustainability implementation strategy delivered to the CHAMP intervention clinics to sustain the implementation of Collaborative Care for OUD co-occurring with MHD.
 
Exploratory Hypothesis: CHAMP intervention clinics receiving the high-intensity sustainability implementation strategy will maintain their implementation outcomes (adoption, reach, intervention fidelity and effectiveness) after the effectiveness trial has been completed (post) compared to during the effectiveness trial (pre).

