PTSD – Posttraumatic Stress Disorder

SCL-20 - Hopkins Symptom Checklist

WFS – Written For Study

Mediator variables

The hypothesized mechanism of action is engagement in MOUD, which we define as initiation and “consistent” refilling of the MOUD medication, which has been demonstrated to be correlated with good outcomes.¹² MOUD consistency is defined as the ratio of the number of days they reported taking the MOUD medication (numerator) to the number of days during the reporting period for which it was prescribed (denominator).¹² This is measured from self-reported MOUD use in the past 30 days which is assessed using survey questions written for the study.

4. Analyses

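### The mediation analysis pairs MOUD consistency with outcomes from the same survey wave (for opioid use, the same 30 days), so its indirect effect cannot show direction; lagged rows should be added and the conclusion limited

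*SAP*

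**What the plan says.** The hypothesis is causal and ordered. Protocol section 3 lists under the primary objective that "Persistent use of MOUD will completely mediate any improvements in patient-reported outcomes" seen in intervention clinics. SAP section 4.2 restates it: "MOUD consistency will fully mediate any improvements in patient-reported outcomes observed in intervention clinics compared to control clinics". It describes a chain in which care managers encourage MOUD, MOUD use rises, and outcomes then improve.

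SAP section 3 defines MOUD consistency as days taken divided by days prescribed in the reporting period: "This is measured from self-reported MOUD use in the past 30 days which is assessed using survey questions written for the study". The opioid outcome is the BAM-R item: "In the past 30 days, how many days did you use any of the following drugs". On timing, "Both primary outcomes are assessed at the 6-month follow-up survey", with the 3-month values as secondary outcomes. SAP Table 1 marks mediator and outcomes at baseline, 3 and 6 months.

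For the models, SAP 4.2 says: "Models will be run separately for 3- and 6-months". Path B adds the mediator to the outcome model alongside treatment, and the indirect effect is path A times path B with a bootstrap interval. Table S4b gives each path one 3-month row and one 6-month row. No row pairs a 3-month mediator with a 6-month outcome. SAP 4.2 has no lagged model, no adjustment of path B for earlier-wave follow-up outcomes, and no caveat on direction.

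The protocol defines the mediator differently: in sections 6.1.1, 6.4 and 9.4.3 the ratio covers the 6-month follow-up period, not the past 30 days.

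**The concern.** Randomisation protects path A but not path B. If opioid use resumes in a given 30-day window, a patient may take MOUD on fewer days and report more opioid days in that same window. Path B then picks up a negative association even if MOUD did nothing to opioid use. If the intervention raises MOUD consistency (path A positive), the product A x B comes out negative, which is the direction that the hypothesis predicts.

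The 30-day overlap is documented for opioid use only. The documents give no recall window for the MCS, so for that outcome the point is simply that mediator and outcome come from one survey, with neither measured first.

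At stake is the trial's statement about mechanism: it could report a significant indirect effect, or a larger one than is real, from data that cannot order cause and effect.

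**Working it through.** **Pairing.** The documents state no figure for the mediation analysis, so there is none to reproduce. Same-wave pairing is not stated in so many words, and Figures 2 and 3 are not visible in the text available. It is, however, the only reading that the section 4.2 wording and Table S4b support.

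**Illustration 1: shared cause, no MOUD effect.** All values are assumptions.
- n = 200; latent relapse state R has unit variance and wave-to-wave correlation 0.5.
- Mediator: M = 0.4 x arm - 0.4 x R + error (SD 0.9).
- Outcome: Y = 0.6 x R + error (SD 0.8), with neither M nor arm in it.

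Expected values by hand, leaving out baseline adjustment:
- Within arm, Var(M) = 0.16 + 0.81 = 0.97, Var(Y) = 0.36 + 0.64 = 1.00, and same-wave Cov(M,Y) = -0.4 x 0.6 = -0.24.
- Same-wave: B = -0.24/0.97 = -0.247; A x B = 0.4 x -0.247 = -0.099.
- Lagged (M at 3 months, Y at 6): Cov = -0.24 x 0.5 = -0.12; B = -0.12/0.97 = -0.124; A x B = -0.049.
- Lagged plus 3-month Y: Cov(Y3,Y6) = 0.36 x 0.5 = 0.18; B = (-0.12 + 0.18 x 0.24)/(0.97 - 0.24²) = -0.0768/0.9124 = -0.084; A x B = -0.034.

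The true value is 0 in all three. Simulation (1,000 to 1,500 trials per setting, Monte Carlo 95% interval for A x B) gave means of -0.096, -0.045 and -0.032. Rates of a falsely significant indirect effect:

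| Correlation | Same-wave | Lagged | Lagged + 3-month outcome |
|---|---|---|---|
| 0.3 | 76% | 11% | 7% |
| 0.5 | 74% | about 25% | 14% |
| 0.7 | 72% | 41% | 24% |

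Repeat runs agreed within about 3 percentage points. Adjusting the same-wave model for baseline values made almost no difference (73% against 74%).

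**Illustration 2: opioid use directly lowers MOUD, no MOUD effect.** n = 254 x 155/191 = 206, from the enrolment and the interim follow-up fraction in SAP section 6. Assumptions: persistence of use 0.5, a non-MOUD intervention effect of -0.40 SD, clustering ignored, 2,000 runs. Rates of a falsely significant path B:

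| Reverse effect (SD per SD) | Same-wave | Lagged, baseline use only | Lagged + 3-month use |
|---|---|---|---|
| 0.1 | 43% | 8% | 5% |
| 0.2 | 95% | 22% | 5% |
| 0.3 | 100% | 47% | 5% |
| 0.5 | 100% | 84% | 6% |

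With no reverse effect all three models stay near 5%. Adding 3-month use works fully here because use itself is the cause and is measured. In illustration 1 the cause is latent and the 3-month outcome captures it only in part.

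**What a lag can lose.** Add to illustration 1 a true same-window MOUD effect of -0.4, so the true indirect effect is 0.4 x -0.4 = -0.16. If MOUD use does not carry over between waves, the lagged model estimates -0.056 and is significant in 28 to 29% of trials, close to its 25% under no effect. With the 3-month outcome added, it estimates -0.007 and is significant in 4%. If MOUD use does persist between waves, the lagged model separates the cases: 79% with a true effect against 30% without.

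**The case against.** **The 74% is not a rate of confirming the hypothesis.** A reader might infer that three trials in four would falsely confirm full mediation. They would not. The hypothesis concerns improvements that are observed, and illustration 1 contains none: the arm has no total effect, so the direct effect is 0 - (-0.10) = +0.10 and cancels the indirect one. A significant improvement together with a significant indirect effect occurred in only 0.9% of those trials. If a non-MOUD arm effect of -0.40 is added, the direct effect stays near -0.30 and the spurious part is about 0.10/0.40, a quarter of the total. The pattern that would be read as full mediation (improvement, significant indirect effect, non-significant direct effect) then appears in about 15%. The SAP estimates path C, so a remaining direct effect would be visible. This objection stands in full.

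**The lag is not a cure.** It leaves about 25% false positives without the 3-month outcome and 14% with it, and it can miss a short-acting effect. This also stands, and it argues against making the lagged model the sole analysis.

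**The mediator is a ratio to days prescribed.** A patient with no prescription has no denominator, so stopping MOUD altogether need not lower the ratio as the simulations assume. That limits how literally the percentages can be taken. It does not give the same-wave estimate a direction.

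**The protocol's 6-month window might avoid the overlap.** It does not, because that window contains the 30 days counted in the 6-month outcome.

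**Conclusion.** The point holds for the mediation hypothesis. As planned, the indirect effect mixes any MOUD effect with reverse or shared cause and can be significant when MOUD has no effect on the outcome: about 74% of trials in illustration 1, and a false path B in 43 to 100% in illustration 2. These sizes rest on assumed relapse mechanisms, linear models and no clustering. They show that the problem can be large, not how large it is in this trial.

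The documents do not support reading this as a threat to the primary result: beta_5 compares randomised groups and does not involve the mediator. Nor do they support a 30-day overlap for MCS, or the idea that the data already collected settle direction.

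**What to change.** In SAP 4.2 and Table S4b:

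1. Keep the same-wave 3- and 6-month estimates, labelled as associations that do not establish direction.
2. Add pre-specified rows for 3-month MOUD consistency predicting the 6-month outcome, adjusted for baseline mediator and baseline outcome, both with and without the 3-month outcome.
3. Claim mediation of 6-month outcomes only if the lagged estimates agree with the same-wave ones and path C is reported beside them.
4. Make no directional mediation claim for 3-month outcomes, because no post-baseline mediator measurement precedes them.
5. Reconcile the mediator window: past 30 days in SAP section 3, the 6-month follow-up period in protocol sections 6.1.1, 6.4 and 9.4.3.

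If mediation results have already been seen, date the new rows and say so.

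The cost is SAP wording and extra table rows, with no new data. The SAP should state the limits: the lagged estimates reduce the bias without removing it, are less precise, need both follow-up surveys, and can miss a short-acting MOUD effect if MOUD use does not persist between waves. Adjusting for the 3-month outcome may also remove part of a real early effect, which is why both versions are needed.
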